5.5.1 Clinical Dementia Rating–Global Score (CDR-GS) and Individual Components of the CDR scale

The Washington University CDR is a global assessment instrument that yields global scores (GS) and sum of boxes (SOB) scores. The CDR is derived from a semi-structured interview with the participant and an appropriate informant, and it rates impairment in six categories (Memory, Orientation, Judgment and Problem Solving, Community Affairs, Home and Hobbies, and Personal Care) on a 5-point scale for which 0 = no impairment, 0.5 = questionable impairment, and 1, 2, and 3 = mild, moderate, and severe impairment, respectively. From the six individual category ratings, or box scores, the CDR-GS is established by clinical scoring rules, for which CDR 0 = no dementia and CDR 0.5, 1, 2, or 3 = questionable, mild, moderate, or severe dementia, respectively (Morris 1993).

5.5.2 Dependence Level Assessed by the ADCS-ADL Score

To calculate dependence levels, scores on the ADCS-ADL can be transformed into discrete levels of disability via an algorithm developed initially by Kahle-Wroblewski (2015). Items from the ADSC-ADL were mapped to 6 levels of dependence derived from the Dependence Scale (Zhu et al., 2009), ranging from Level 0: no impairment in instrumental or basic ADLs to Level 5: complete incontinence or inability to transfer. Four subscales were used to aid the construction of dependence levels, including bADLs, domestic/household activities, communication/engagement and outside

activities. The mapping of items to dependence levels was validated using additional clinical and economic measures.

A revised algorithm, developed to a) remove ambiguity regarding the contribution of some items and b) add clarity on the handling of missing data, will be used to calculate the dependence levels. Progression to greater levels of dependence is indicative of disease progression and is informative for a variety of care providers and stakeholders. This algorithm is provided in appendix, see [Appendix 2](#).

5.5.3 Integrated AD Rating Scale (iADRS)

The iADRS is a composite of cognition and function that combines scores from the ADAS-Cog-13 (cognition) and the instrumental component of the ADCS-ADL (function) ([Wessels et al., 2018](#)). A sum score of the total scores of both components is calculated (ADAS-Cog is reversed) using the following formula:

$$iADRS = [-(ADAS-Cog13) + 85] + ADCS-iADL.$$

Total score range from 0 to 141. The iADRS total score will be generated and results may be reported in the CSR.

5.5.4 AD Composite Score (ADCOMS)

The ADCOMS was developed to assess cognition and function in early stages of AD. It is a composite score that combines 12 items from existing AD measures, specifically the ADAS-Cog (Delayed word recall, Orientation, Word recognition, Word finding difficulty), MMSE (Orientation time and Constructional praxis) and all CDR-SB items ([Wang et al., 2016](#)). The ADCOMS score was built using a linear longitudinal model to characterize the relationship between disease progression and the individual items from existing AD clinical scales. A PLS regression procedure was used to identify individual clinical scale items that represent AD-related clinical decline over time to calculate their respective weighting factors. The resulting composite ADCOMS score is a weighted linear combination of the individual scale items selected in the fitted PLS model. Items with small contribution to the PLS model were removed according to Wold's criterion (a Variable Importance of Projection below 0.8). Total score range from 0 to 1.97, with lower scores indicating greater impairment. The ADCOMS total score will be generated and results may be reported in the CSR.

5.5.5 Quality of Life–Alzheimer’s Disease (QoL-AD)

The Quality of Life–Alzheimer’s Disease (QoL-AD) was developed to assess quality of life (QoL) in participants who have dementia ([Logsdon et al. 1999](#), [Logsdon et al 2002](#)). The QoL-AD consists of 13 items covering aspects of participants’ relationships with friends and family, physical condition, mood, concerns about finances, and overall assessment of QoL. The total score is the sum of the 13 items and ranges from 13 to 52, with higher scores indicating better health-related QoL. In this study, the QoL-AD

will be administered in a standardized, structured interview format to participants by investigative staff in order to gather participant responses about QoL. The study partner will also complete the study partner version of the questionnaire to enable proxy responses from the study partner.

5.5.6 Neuropsychiatric Inventory Questionnaire

The Neuropsychiatric Inventory-Questionnaire (NPI-Q) ([Kaufer et al. 2000](#)) was developed to assess a wide range of behaviors encountered in dementia participants, to provide a means of distinguishing severity of behavioral changes, and to facilitate rapid behavioral assessment through the use of screening questions. It is an informant-based instrument in which 12 behavioral domains are evaluated. The recall period is the past month, and severity scores range from 0 to 36, with higher scores indicating greater severity. The study partner's distress portion of the scale was not used in this study.

5.5.7 Zarit Caregiver Interview–Alzheimer's Disease (ZCI-AD)

The Zarit Caregiver Interview-Alzheimer's Disease (ZCI-AD) is a modified version of the Zarit Burden Interview 22-item version, which was originally designed to reflect the stresses experienced by caregivers for people with dementia ([Zarit and Zarit 1990](#)). The modified version includes modifications in item and title wording (e.g., removal of "your relative" to refer directly to the participant, removal of "burden" from title), inclusion of additional items, the use of 11-point numerical rating scales for each item and a 4 week recall period. The ZCI-AD measure consists of 27 items covering 13 domains (i.e., humanistic impact domain (14 items) including the domains physical (3 items), emotional (4 items), social (3 items), and daily life (4 items), and the additional domains exhaustion (2 items), dependence (2 items), worry (2 items), role perception (3 items), financial impact (1 item), difficulty with medication (1 item), overall difficulty of caregiving (1 item), and sadness (1 item)). The ZCI-AD is completed by the study partner without involvement from the site staff. The ZCI-AD is scored on a domain level with each domain score ranging from 0 to 100 with higher scores indicating higher level of impact. All item responses are re-coded on a 0 to 4 scale (response category 0=0; response category 1,2, and 3=1; response category 4,5,and 6=2; response category 7 and 8=3; response category 9 and 10=4) and items of a domain are summed up and transformed to 0 to 100 score range. Domain scores are only calculated if responses of at least 80% of items of the respective domain are available. The ZCI-AD has been validated in prodromal, mild and moderate stages of AD ([Bernards, C et al.](#))

5.6 SAFETY ANALYSES

Descriptive statistics will be used to analyze all safety data collected in the double-blind treatment period in the safety-evaluable analysis set, unless otherwise specified.

Safety data collected from the day of the first dose of blinded study drug up to 14 weeks after the last dose of blinded study drug (but no later than the day before the first OLE dose for the participants who entered the OLE period) will be included in the

beyond the 14-week post last dose period and until the end of the study will be included in the follow-up period analyses.

For participants who entered the OLE period, safety data collected from the day of the first OLE dose up to 14 weeks after the last OLE dose will be included in the OLE period analyses

Safety analyses will be assessed through summaries of exposure to study treatment, adverse events, changes in laboratory test results (including shift tables), MRI findings, changes in vital signs and ECGs, and changes in C-SSRS scores.

5.6.1 Extent of Exposure

Exposure to study drug information will be descriptively summarized by treatment as follows:

- Treatment duration (in weeks)
- Total number of administrations
- Total cumulative dose (mg)
- Number of dose-administrations at each dose level

5.6.2 Adverse Events

All verbatim AEs terms will be coded using the Medical Dictionary for Regulatory Activities (MedDRA) version that is current at the time of the analysis (Version 25.0 or higher), and AE severity will be graded according to the scale defined in Table 5 in Section 5.3.3 of the study protocol (mild/moderate/severe). For each treatment group, the frequency of each AE preferred term will be defined as the number of participants experiencing at least one occurrence of the event. Each table will present the overall number and percentage of participants experiencing at least one AE and the total number of AEs reported. Percentages will be based on the number of participants in the safety-evaluable analysis set. In summary tables, AEs will be sorted by body system (in decreasing order of overall incidence), then by preferred term (in decreasing order of overall incidence). The summary tables will be restricted to treatment-emergent AEs, i.e., AEs that occur on or after the day of first dose of study drug. Non-treatment-emergent AEs (with onset before the first dose) will be listed.

The following safety information will be summarized by treatment group for the double-blind treatment period:

- AEs, AEs by intensity, AEs related to study drug
- Deaths
- SAEs, SAEs related to study drug
- AEs leading to discontinuation of study treatment

- AEs leading to dose modifications (dose interruption, dose reduction or delayed up-titration). Delayed up-titration at any given visit is defined as the simultaneous occurrence of the following two tick-boxes in the eCRF Adverse Events form:
 - Action take with Gantenerumab due to AE/SAE: Dose Not Changed
 - Was dose regimen modified from protocol schedule? Yes"
- Injection site reaction (ISR) signs and symptoms
- Systemic injection reactions (AEs with eCRF tickbox “systemic injection reaction” selected)
- ‘Hypersensitivity reactions’

Protocol-specified adverse events of special interest (AESI) will be listed.

The impact of the COVID-19 pandemic on the safety data will be assessed by reviewing the following:

- Confirmed or suspected COVID-19 AEs
- AEs associated with COVID-19
- Potential long COVID-19 symptoms

The following data handling rules will be applied for all AE summary tables:

- Events that are missing both at onset and at end dates will be considered to have started after the first dose of study drug and the duration will be set to missing.
- If the onset date is missing, and the end date is on or after the first dosing date or unresolved or missing, then the event will be considered to have started after the first dose of study drug.

The following data handling rules will also be applied for specific tables:

- An AE will be included in the summary table of AEs leading to study drug discontinuation if the “action taken with blinded gantenerumab” drop-down menu on the AE eCRF is checked “drug withdrawn”.
- In the summary table of AEs by intensity, if a participant has more than one occurrence of an event, the event with the most severe intensity will be counted. If the intensity of an AE is missing, then the AE will be included only in the total number of events column, and not in the count of participants with the event by intensity.
- In the summary table of AEs related to study drug, if a participant has more than one occurrence of an event, the related event will be counted if applicable. If the relationship of an AE is missing, then the AE will not be included.

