### 5.3.4 Assessment of Causality of Adverse Events

Investigators should use their knowledge of the participant, the circumstances surrounding the event, and an evaluation of any potential alternative causes to determine whether an adverse event is considered to be related to the study drug, indicating “yes” or “no” accordingly. The following guidance should be taken into consideration:

- Temporal relationship of event onset to the initiation of study drug
- Course of the event, with special consideration of the effects of dose reduction, discontinuation of study drug, or reintroduction of study drug (as applicable)
- Known association of the event with the study drug or with similar treatments
- Known association of the event with the disease under study
- Presence of risk factors in the participant or use of concomitant medications known to increase the occurrence of the event
- Presence of non-treatment-related factors that are known to be associated with the occurrence of the event

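### Adverse events with missing causality are left out of the related-AE table and not counted anywhere, so the related-AE incidence in each arm can be understated

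*SAP*

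**What the plan says.** SAP 5.6.2 (Adverse Events) plans summaries by treatment group that include "AEs, AEs by intensity, AEs related to study drug" and, as a separate item, "SAEs, SAEs related to study drug". Among its table-specific data handling rules is one for the related-AE table. For a participant with repeated occurrences, it takes the related one where there is one. It then adds: "If the relationship of an AE is missing, then the AE will not be included". No footnote, row for missing values, listing or sensitivity count is stated for the events left out. No missing-causality rule is stated for the related-SAE table.

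The same section handles other gaps as follows:
- **Both dates missing:** "Events that are missing both at onset and at end dates will be considered to have started after the first dose of study drug".
- **Onset missing, and the end date after first dosing, unresolved or missing:** "then the event will be considered to have started after the first dose of study drug".
- **Intensity missing:** "If the intensity of an AE is missing, then the AE will be included only in the total number of events column"; the event is left out of the participant counts by intensity.

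Outside the safety section, SAP 5.3.2 (Table 3) classes a treatment withdrawal with an uninformative reason as study drug or condition related. It also puts all AE withdrawals in that class and calls this conservative.

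On data collection, Protocol 5.3 requires a causality assessment for each recorded event. Under Protocol 5.3.4 the investigator is to "determine whether an adverse event is considered to be related to the study drug", answering yes or no.

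**The concern.** A related-AE table is read as the number of participants with an event that the investigator attributed to the drug. Under the stated rule, an event with no recorded attribution contributes nothing to that number, and the reader cannot tell whether none or several were set aside. The omission works in one direction within an arm. It also sits oddly beside the date rules in the same section, which bring an event of unknown timing into the treatment-emergent tables, and beside Table 3, which assigns an unexplained withdrawal to the drug or condition. The SAP gives no reason for the different choice here.

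At stake is the accuracy of one descriptive safety table. If the rule is carried over to serious events, a second table is affected.

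**Working it through.** The plan gives no rate of missing causality and no expected related-AE rate, so there is no stated figure to reproduce. The direction follows from the rule; the size can only be illustrated.

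**Direction within an arm.** Let p be the share of participants with a truly related AE, u the share with unrelated AEs only, and m the fraction of causality fields missing. Take one AE per participant, with values missing at random within an arm.
- SAP rule: reported share L = p(1 − m), which is at most p.
- Missing counted as related: reported share U = p + u·m, which is at least p.

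The two agree when m = 0. With several occurrences, a participant with another occurrence of the event recorded as related is still counted, so the shortfall is smaller than this model implies.

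**Size per participant.** SAP 1.2 plans 508 per arm. The actual denominator is the safety-evaluable set by treatment received, so 508 is approximate. One participant with a missing-causality AE and no AE recorded as related lowers the incidence by 1/508 = 0.20 points. Five, chosen only for illustration, lower it by 5/508 = 0.98 points.

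**Illustration over a range of m.** Assumed, not from the documents: p = 30% active and 10% placebo; u = 55% and 75%. True counts are 508 × 0.30 = 152.4 and 508 × 0.10 = 50.8, a difference of 20.0 points.

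| m, both arms | SAP rule, active / placebo | Difference | Missing as related, active / placebo | Difference |
|---|---|---|---|---|
| 1% | 150.9 / 50.3 | 19.8 | 155.2 / 54.6 | 19.8 |
| 5% | 144.8 / 48.3 | 19.0 | 166.4 / 69.9 | 19.0 |
| 10% | 137.2 / 45.7 | 18.0 | 180.3 / 88.9 | 18.0 |

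The equal differences under the two rules come from an assumption: p + u = 85% in both arms. The difference under the second rule is (0.30 − 0.10) + m(0.55 − 0.75) = 0.20(1 − m), the same as under the first.

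With lower assumed rates (p = 10% and 5%; u = 75% and 80%), true counts are 50.8 and 25.4. At m = 10% the SAP rule gives 45.7 and 22.9, and counting missing as related gives 88.9 and 66.0. The difference is 4.5 points under either rule, against a true 5.0.

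**Unequal missingness (30% / 10% case).**
- 5% missing in the active arm only: SAP rule 28.5 − 10.0 = 18.5 points; missing as related 32.75 − 10.0 = 22.75.
- 5% missing in placebo only: SAP rule 30.0 − 9.5 = 20.5 points; missing as related 30.0 − 13.75 = 16.25.

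So the SAP rule can shrink or widen the between-arm difference, and so can the alternative.

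**What by-arm numbers add.** With L and U known for each arm, the difference lies between L(active) − U(placebo) and U(active) − L(placebo). At m = 1% that is 29.7 − 10.75 = 18.95 to 30.55 − 9.9 = 20.65 points. At m = 10% it is 27.0 − 17.5 = 9.5 to 35.5 − 9.0 = 26.5. Neither table alone shows this range.

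**The case against.** The best defence is that the SAP does not impute investigator judgements. Missing intensity is not set to severe, and missing causality is not set to related. The date rules do a different job: they decide whether an event enters the treatment-emergent tables at all. That is fair, and it means the SAP contains no general worst-case standard that this rule breaks. It does not remove the difference in visibility: an event without intensity stays in its table's total, whereas an event without causality leaves the related-AE table without trace.

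Second, counting missing as related can be further from the truth. At 10% missing in the main illustration, the SAP rule errs by −15.2 and −5.1 participants (137.2 against 152.4; 45.7 against 50.8). The alternative errs by +27.9 and +38.1 (180.3 and 88.9), and the difference of 18.0 points is no better. This stands, and it is why the by-arm footnote is an essential part of the fix.

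Third, missing values should be few, given the required yes/no answer and the sponsor's queries on discrepant data (Protocol 7.1). This also stands and keeps the point minor.

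A reader might infer more than the documents support:
- **That these events disappear from the safety report.** They remain in the all-AE summary and, where applicable, those for SAEs, deaths, discontinuations and dose modifications. ARIA is analysed mainly from MRI findings (SAP 5.6.3), and injection-site reaction signs and symptoms are summarized separately.
- **That related SAEs will be under-reported.** The rule names only the related-AE table; its reach to the SAE table is unstated.
- **That the comparison is tilted in favour of the drug.** The same rule applies to both arms, and the working shows that the difference can move either way.
- **That a formal conclusion is affected.** SAP 5.6 makes the safety analysis descriptive.

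**Conclusion.** The point holds as a limited one. The rule can lower the related-AE incidence in each arm or leave it unchanged, and cannot raise it. As written, the plan gives the reader no means of seeing how many events were set aside. It is less cautious than the SAP's handling of missing onset dates and uninformative withdrawals, though consistent with its refusal to impute missing intensity.

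The size is unknown because no missing rate is given. It is about 0.20 points of incidence per participant affected, on a denominator of 508. With 1% missing, the assumed active-arm count moves only from 152.4 to 150.9. Those counts rest on assumed event rates, one AE per participant and missingness at random within an arm. The direction within an arm needs none of these assumptions. The reach of the rule to related SAEs is an open question in the text, not a demonstrated omission.

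**What to change.** Replace the sentence in SAP 5.6.2 with a rule that applies to both the related-AE and the related-SAE tables:
- Count an event with missing causality as related.
- Footnote, by arm, the number of such events and the number of participants who enter the table only because of one. Subtracting that participant number gives the figure without them.

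This needs one line of SAP wording and a footnote, and no new data. If no causality values are missing, the tables do not change. The cost is that the related rate may be somewhat overstated in both arms, and could look slightly less favourable. The by-arm footnote shows by how much.

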5.6.3 Magnetic Resonance Imaging Safety Findings

ARIA-E and ARIA-H are identified risks associated with gantenerumab. Sites were asked to capture all ARIAs as AEs in the eCRF that met any of the following criteria:

- Symptomatic ARIA-E (i.e., accompanied by CNS symptoms), and/or

- ARIA findings that result in a change in study treatment (e.g., dosage modification, treatment interruption, or treatment discontinuation), and/or
- Findings that are otherwise clinically significant in the investigator’s judgment

Not all ARIA MRI findings qualify as AE. ARIA analyses will be mainly based on ARIA MRI findings. ARIA AEs will also be reported. Based on MRI data, the incidence, and severity (based on the Barkhof Grand Total Score [BGTS]) ARIA-E and the incidence of ARIA-H will be summarized by treatment group and within this also by APOE ε4 genotype (by number of alleles) and by dose level. Additionally, the timing of ARIA-E and the timing to meet the protocol-defined criteria for permanent discontinuation due to ARIA-H will be also summarized by descriptive statistics and eventually by Kaplan-Meier methods. Recurrence of ARIA-E will be summarized by treatment group and within this also by APOE ε4 genotype (by number of alleles). ARIA-E associated with CNS symptoms (see Section 5.6.3.1) and with serious CNS symptoms will be summarized by treatment group and within this also by APOE ε4 genotype. Temporal co-occurrence of ARIA-E and ARIA-H will be summarized by treatment group and within this also by APOE ε4 genotype (by number of alleles). Temporal co-occurrence is defined as an MRI scan showing new ARIA-H that occurs between ARIA-E onset and resolution (inclusive), irrespective of the brain region.

MRI findings other than ARIA will also be summarized.

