##### **4.3.2.1 Gantenerumab and Placebo Administration during Double-Blind Treatment Period**

Gantenerumab or placebo will be administered by SC injection to all participants.

Gantenerumab will be administered by SC injection to all participants randomized to the active treatment arm, regardless of *APOE*  $\epsilon$ 4 status, at a dose of 120 mg SC Q4W for 3 months, 255 mg SC Q4W for 3 months, and 510 mg SC Q4W for 3 months, prior to reaching the target dose (see Figure 8). Once the target dose is reached, study drug will be administered every 2 weeks (Q2W administration of 510 mg SC gantenerumab). The switch to a Q2W administration schedule allows decreasing the number of SC administrations in the abdomen per visit.

Note: A minimum of 3 doses during each dosing step must be administered prior to up-titration.

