## Appendix 1 Schedule of Activities (cont.)

**Table 2: Week 36 to the End of Study: 510 mg Q2W**

Assessment/Procedure												Only for Participants Who Have Completed Week 104 when the 12 week study extension is Implemented		Early Term Visit a	Unsched Visit	
	Treatment Period											Final Efficacy and Safety Assessments	Follow-Up Period for Participants Not Enrolling in the OLE			
	Wk 36	Wk 38	Wk 40	Wk 41	Wk 42–50	Wk 52	Wk 54–74	Wk 76	Wk 78–102	Wk 103	Wk 104 a, b	Wk 116	Wk 152			
Dose number	10	11	12		13–17 c	18 a	19–29 c	30 a	31–43 c							
Dose level in milligrams (mg)	510	510	510		510	510	510	510	510							
12-Lead ECG						B		B			x	x		x	x	
PK plasma sample d				x (Site visit)		B		B		x (Site visit)		x	x	x	x	
ADA sample						B		B				x	x	x	x	
Clinical RNA sample											x			x		
Serum chemistry e and hematology f						B		B			x	x	x	x	x	
Plasma biomarker sample o						B					x			x	x	
Complete physical examination (including neurological systems) g											x			x	x	
Limited physical examination h						B		B							x	
Weight						x		x			x	x	x	x	x	

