## Appendix 5 Amyloid-Related Imaging Abnormality Hazard Model

### 1. BACKGROUND

Hutmacher et al. (2013) presented a pharmacodynamic (PD) model for bapineuzumab addressing the first occurrence of amyloid-related imaging abnormalities, or ARIAs, of “vasogenic edema” (ARIA-E) events. Patients received constant dose regimens of 0.5, 1, and 2 mg/kg given every 13 weeks over 1.5 years. A total of 2435 patients with 243 ARIA-E events were analysed. As shown below, a log hazard model was developed that included three elements:

- A baseline value ( $I_{BS}$ ) reflecting a constant ARIA-E hazard for apolipoprotein E allele  $\epsilon 4$  (*APOE*  $\epsilon 4$ ) gene carriers and non-carriers, respectively
- Plasma drug concentrations ( $c$ ) of bapineuzumab modulating the ARIA-E hazard through the maximum effect ( $E_{max}$ ) of drug and 50% of the effective concentration ( $EC_{50}$ ) parameters
- A time component continuously suppressing the ARIA-E hazard by the time ( $t$ ) since first dosing.  $ET_{50}$  and  $\gamma$  modulated this effect.

$$\log h(t) = I_{BS} + \frac{E_{max} \cdot c(t)}{c(t) + EC_{50}} \cdot \frac{ET_{50}^{\gamma}}{ET_{50}^{\gamma} + t^{\gamma}}$$

Because no model parameters were reported in Hutmacher et al. 2013, the parameters were derived from predicted time-concentration and time-hazard curves presented in Hutmacher et al. 2013 after digitizing the respective graphs for 0.5 mg/kg in *APOE*  $\epsilon 4$  carriers.  $I_{BS}$  parameters were obtained from the graphs directly, whereas the other parameters were calculated from the digitized data using MATLAB (or matrix laboratory) and maximum likelihood estimation. Parameter values are shown in [Table 1](#).

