shown to be ineffective in Studies WN25203 (SCarlet RoAD) and WN28745 (Marguerite RoAD).

- A 20% difference is the usual acceptability threshold to establish PK bioequivalence. The protocol includes 20 dose-months (80 weeks) at target dose after the up-titration period. Missing less than 4 dose-months results in an overall reduction in drug exposure of less than 20% of the total planned dose.

As a conservative approach, all withdrawals from study treatment due to an AE will be classified as SDCR for the purpose of the primary analysis. This includes withdrawal from study treatment due to suspected or confirmed COVID-19 infection AE, because the relationship of these events to the participant condition may be ambiguous.

All SDCR ICEs will be handled with a treatment policy strategy, while NSDCR ICEs will be handled with a hypothetical strategy. The frequencies of ICE will be summarized by treatment arm.

In this study, given the disease stage at baseline of the target population, death is expected to be a rare event and mostly not considered related to treatment or disease progression, and as such the corresponding ICE of death will be handled with a hypothetical strategy for the primary estimand. Of note, a supplementary estimand which defines all ICEs, including death, as SDCR (and thus using the same imputation strategy as for the other SDCR ICEs; see Section 5.3.3), is described in Section 5.3.5.

Table 3 Intercurrent Events Impacting Primary Analysis

| Intercurrent Event | SDCR/NSDCR | Estimand Approach |
|--|------------|-----------------------|
| Withdrawal from study treatment due to lack of efficacy | SDCR | Treatment Policy |
| Withdrawal from study treatment due to safety or tolerability reason (NOTE: This will include discontinuation due to AE, incl. suspected or confirmed COVID-19 AEs) | SDCR | Treatment Policy |
| Withdrawal from study treatment with no informative reason given | SDCR | Treatment Policy |
| Withdrawal from study treatment due to the COVID-19 pandemic | NSDCR | Hypothetical Strategy |
| Substantial reduction in drug exposure due to the COVID-19 pandemic (defined as ≥ 4 missed dose-months) | NSDCR | Hypothetical Strategy |
| Withdrawal from study treatment due to purely administrative reason | NSDCR | Hypothetical Strategy |
| Death | NSDCR | Hypothetical Strategy |
| Withdrawal from study treatment due to use or initiation of protocol prohibited medication | SDCR | Treatment Policy |

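### ARIA incidence by dose level has no exposure adjustment, although the scheduled levels last 12, 12, 12 and 80 weeks

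*SAP*

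**What the plan says.** SAP 5.6.3 bases the ARIA analyses mainly on MRI findings. ARIA-E incidence and severity and ARIA-H incidence "will be summarized by treatment group and within this also by APOE ε4 genotype (by number of alleles) and by dose level". The timing of ARIA-E is to be "summarized by descriptive statistics and eventually by Kaplan-Meier methods", but not by dose level. SAP 5.6.1 lists "Number of dose-administrations at each dose level" among the exposure summaries, and it does not define the levels either.

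Protocol 4.3.2.1 sets the titration as "120 mg SC Q4W for 3 months, 255 mg SC Q4W for 3 months, and 510 mg SC Q4W for 3 months", followed by 510 mg Q2W. SAP 5.3.2 gives the length of the last phase: "The protocol includes 20 dose-months (80 weeks) at target dose after the up-titration period". In Appendix 1, the row that begins "Dose level in milligrams (mg" prints 510 both for Weeks 24 to 32, given Q4W (Table 1), and for every dosing visit in the table titled "Week 36 to the End of Study: 510 mg Q2W".

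The protocol expects ARIA-E risk to change over time. Section 1.2.3 reports that new ARIA-E in the earlier prodromal study was most frequent between 3 and 6 months and much rarer after the first year. Appendix 5 includes in its hazard model "A time component continuously suppressing the ARIA-E hazard by the time" since first dose.

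**The concern.** A proportion of participants with ARIA at each level depends on how long they spend at that level. Here one level is nearly seven times as long as each of the others (80/12 = 6.7), and the hazard is expected to be low for most of it. A reader who uses the table to see where along the titration the risk lies could be pointed to the long maintenance phase when the weekly risk is highest during the second and third steps. The protocol's risk mitigation is slow titration with an MRI before each increase, so this is what readers will look for in the table. If 510 mg were tabulated as one level, the last titration step would also be merged with a regimen of twice the monthly dose.

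**Working it through.** **Inputs.**
- PK (Appendix 4 Table 1): two compartments, CL 0.336, V2 3.52, Q 0.869, V3 6.38, KA 0.22, F 0.494.
- Doses: the G3-equivalent regimen in Protocol 1.3.2, on whose material the models were built: 150, 300 and 600 mg Q4W (three doses each), then 600 mg Q2W from Week 36 to Week 114.
- Hazard (Appendix 5 Table 9): I_BS 3.52E-5 (carrier) or 2.14E-5 (non-carrier), Emax 5.92, EC50 6.78, ET50 323.44 days, γ 2.15.

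**Formula.** h(t) = I_BS × exp{[Emax·c/(c+EC50)] × [ET50^γ/(ET50^γ+t^γ)]}, S(t) = exp(−∫h). I_BS is read as a daily hazard, because values of that size cannot be log hazards as printed. The calculation is for a typical participant with no dosing delays.

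**Reproducing the plan's figure.** Cumulative ARIA-E to Week 104 is 29.9% in carriers and 19.4% in non-carriers. The documents give no carrier share. Assuming 60%, the total is 0.6 × 29.9 + 0.4 × 19.4 = 25.7% (24.7 to 26.8% for 50 to 70%), against about 26% in Protocol 1.3.2.

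**By level.** Incidence = S(start) − S(end). Rate = incidence divided by person-years at risk, ∫S dt over the level.

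| Carriers, Table 9 | Weeks | Incidence, % | Person-years per 100 randomized | Rate per 100 person-years |
|---|---|---|---|---|
| 120 mg Q4W | 0–12 | 4.6 | 22.5 | 20.5 |
| 255 mg Q4W | 12–24 | 8.9 | 20.8 | 42.5 |
| 510 mg Q4W | 24–36 | 7.4 | 18.9 | 39.2 |
| 510 mg Q2W | 36–116 | 9.5 | 110.8 | 8.6 |
| 510 mg as one level | 24–116 | 16.9 | 129.7 | 13.0 |

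Non-carriers, same order: incidence 2.8, 5.6, 4.9, 6.5 and 11.3%; rates about 12, 26, 24, 5 and 7.7.

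**Does an at-risk denominator remove it?** No. Among carriers event-free at entry the proportions are 4.6%, 8.9/95.4 = 9.3%, 7.4/86.5 = 8.6% and 9.5/79.1 = 12.0%; 510 mg as one level gives 16.9/86.5 = 19.5%.

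**Sensitivity.** With 510 mg as one level, it has the highest incidence and lowest rate under all four gantenerumab parameter sets (Appendix 5 Tables 3, 5, 7 and 9), in both genotype groups and with either printed V2 (3.52 or 3.152). With regimens split, 510 mg Q2W has both under Tables 3, 7 and 9. Under Table 5, carriers have 4.5, 8.8, 6.3 and 5.7%: Q2W still has the lowest rate (4.9), but 255 mg has the highest incidence. Using the actual doses × 1.18 instead changes the 120 mg carrier figures to 4.3% and 18.9, with no change in order.

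**Within the Q2W period** (carriers, Table 9), the rate is 23 in Weeks 36–48, 12 in Weeks 48–60, 7 in Weeks 60–76 and 3 in Weeks 76–116.

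**The case against.** The strongest objection is that little of this is an error in the plan.

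- Incidence while on a regimen is a legitimate safety quantity, and high cumulative incidence with a low rate is not a contradiction.
- Placebo follows the same schedule, so comparing arms within a level is fair as to scheduled duration.
- Titration is the same for everyone, so apart from delays an overall Kaplan-Meier curve maps onto the steps.
- SAP Sections 1 and 6 leave layouts, datasets and programs to Data Analysis Plan Modules 2 and 3, where a denominator may be set.
- No test or decision rule depends on the table, and the iDMC reviews ARIA unblinded.

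All of this stands and limits the consequence. It does not make the by-level table readable as a comparison between levels. The denominator and assignment rule are also methods that belong in the SAP.

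A reader might infer that the SAP plans to merge 510 mg Q4W with Q2W. The documents do not say so. The inference rests on one row label in the schedule. Protocol Table 1 shows dosing frequency on a separate row, Protocol 3.2 describes the move to target dose as an uptitration, and an MRI is scheduled before the Week 36 dose. The term is undefined, and that is as far as the point goes.

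A simple rate per regimen would also mislead. One rate for all 80 weeks of Q2W would print about 9 against 21 for 120 mg, although the first 12 weeks at target (23) are at least as high as 120 mg.

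**Conclusion.** The point holds as a reporting weakness that is cheap to repair. Unadjusted incidence by level can order the titration steps differently from the underlying rates. In carriers under Table 9, 510 mg Q2W has the highest incidence (9.5%) and the lowest rate (about 9 per 100 person-years at risk), while 255 mg and 510 mg Q4W have rates of about 42 and 39. If 510 mg is treated as one level, it shows 16.9% and 13.0.

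The result assumes the protocol's hazard model with I_BS as a daily hazard, typical PK and no delays. The 12-week steps are scheduled minimums, so real durations will vary. With 510 mg as one level the reversal holds for all four parameter sets; with regimens split it is only partial under Table 5.

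A reader might extend the claim to ARIA-H, since the table covers both. The documents give no ARIA-H hazard model, so no reversal is shown there. Nor does the point touch the primary analysis, type I error, or any dosing or clinical rule.

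**What to change.** In SAP 5.6.3 and 5.6.1:

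1. Define the levels as four regimens: 120 mg Q4W, 255 mg Q4W, 510 mg Q4W and 510 mg Q2W.
2. Assign each event to the regimen of the last dose before the detecting MRI. Scans scheduled before the Week 12, 24 and 36 doses fall at the step boundaries, so the rule is workable.
3. Beside the counts, give first-event ARIA-E and ARIA-H rates per 100 person-years at risk, by arm and APOE ε4 genotype.
4. Split the Q2W period at scheduled MRIs, for example Weeks 36–48, 48–60, 60–76 and 76–116, so that a falling hazard is not averaged over 80 weeks.

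The cost is some SAP wording and a few extra rows and columns, using dosing and scan dates already collected. The downside is that onset is interval-censored. Scans are 12 weeks apart up to Week 60, then 16 weeks (60 to 76) and 28 weeks (76 to 104). Late rates are therefore approximate and may miss events that resolve between scans, and a table footnote should say so. No dosing or clinical rule changes.
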